Participants will then complete a post-training questionnaire, rating their competence to implement aspects of the NTPC intervention and the quality and/or utility of the received training protocol.

After training, participants will simulate aspects of the intervention (with mock clients, either researcher or actor). The simulation will take place at the end of the in-person training period. Participants will then complete a post-simulation questionnaire, again rating their competence to implement aspects of the NTPC intervention and the quality and/or utility of the received training protocol. Participants will be given an option of demonstrating aspects of the NTPC intervention with their own child/client at the end of the training session after simulation.

The baseline questionnaire will be completed prior to training on the same day as the training session or no more than one week in advance of the in-person training session. The post-training questionnaire will be completed on the same day as the in-person training. The post-simulation questionnaire will be completed on the same day as the in-person training or no later than two days post in-person training/simulation session.

The time requirement for participants is expected to be no more than 8 hours.

	e.	Estimated	Time	Commitment for	· Partici	pants
--	----	-----------	------	----------------	-----------	-------

1 in-person session	Number of sessions for each participant	
4-8 hours	Time commitment per session for each participant	
8	Total time commitment for each participant	

f. Access to Existing Data: If you are analyzing existing data, records, or specimens, explain the source and type, means of access, and permission(s) to use them. If not accessing existing data, indicate "NA"

N/A		

- **2. SUBJECTS:** *Provide your best estimates below.*
 - a. Age Range of Subjects Included: 18-65

	. Number:		
((Indicate a range, or maximum, if exceeded, you will	· · · · · · · · · · · · · · · · · · ·	
	15 Male2	Female 40 Total	
c.	Target Population: Describe your target population children ages 9-12, healthy adults 18 or over, etc.)		

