	you have any conflict of interest (financial, personal, employment, dual-role) that could feet human subject participation or protection? Dual-role examples: faculty-student (does not			
	ply to action research projects for education students), medical practitioner-patients, supervisor-			
dir	rect reports, etc.			
	Yes X No			
IC.	Vos. plansa indicata the stans you will take to minimize any undue influence in your research			
	Yes, please indicate the steps you will take to minimize any undue influence in your research, cruitment and consent process. You can also reference the university Financial Conflict of			
	terest policy: https://www.stkate.edu/pdfs/orsp-policy-fcoi.pdf			
	currently have no conflict of interest, however there may be appearance of a financial conflict of interest.			
	s a part of the research study I as principle investigator will be examining the sleep care positioning are giver training program developed through my dissertation work as well as in my role as master's project			
	dvisor. An aspect of the training program involves information on sleep care positioning systems and			
m	nethods for how to properly use such positioning devices.			
	a addition to my employment at St. Catherine University I am also employed as a sleep care positioning			
	onsultant by a small for-profit business, Bridgeway Independent Living Designs (BILD) LLC, that sells eep care positioning systems. In this consultant position, I am paid a flat rate (non-commission) to evaluate			
	and educate clients/potential clients about the risks and benefits of the nighttime postural care / sleep care			
	ositioning intervention.			
	While there is no conflict of interest, based on definitions provided in the St. Catherine University Office of			
	esearch and Sponsored Programs' Financial Conflict of Interest Policy, there may be the appearance of a nancial conflict of interest. For instance, if participants are interested in purchasing a sleep care positioning			
	system and they are aware of my employment with BILD, BILD may indirectly benefit due to participants			
	new knowledge about the small business. This is not a financial conflict of interest, since my employment /			
	elationship with BILD does not have the potential to "directly and significantly affect the design, conduct or			

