I re	eporting" of the research (p. 3). In my role as primary investigator I'll be representing St. Catherine niversity, not BILD. BILD is not providing any funding for the research. To reduce potential for conflict			
	f interest, BILD will not be identified in any of the sleep care positioning caregiver training program			
	naterials or research participant recruitment / research related documents. It is possible that research			
	participants may already be aware / or become aware of my consultant work during the research period. If persons in their role as participants inquire about BILD I will remind participants that I'm representing St.			
	atherine University, in my role as PI on the study and that any further questions about BILD can be			
	ddressed after the data collection period has ended.			
	•			
DECD	UITMENT: LOCATION OF SUBJECTS (Select all that apply):			
KECK	COTTMENT. LOCATION OF SUBSECTS (Select all that apply).			
	St. Catherine University students			
	School setting (PreK – 12)			
	Hospital or clinic			
	Other Institution			
	(Specify):			
X	None of the above (Describe location of subjects):			
	(Specify):			
	A convenience sample of care providers from two different organizations have expressed			
	interest in the study. Other care providers known to the PI whom might be interested in this			

3.

research study may also be recruited for participation. Care providers working at the following twin cities organizations have identified initial interest: Gillette Children's Specialty Healthcare and LiveLife Therapy Solutions, Inc. Note: If identified recruitment efforts fail to produce the desired number of participants, flyers may also be delivered via email or posted as hard copy in health-based programs at St. Catherine University and University of Minnesota.

NOTE: If subjects are recruited or research is conducted through an agency or institution other than St. Catherine University, submit either written or electronic documentation of approval and/or cooperation. An electronic version should be sent from the email system of that particular institution. The document should include the name of the PI, Title of the approved study, as well as the name and title of the appropriate administrator sending the approval. You should include an abstract/synopsis of your study when asking for approval from an external institution.

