a. Recruitment Method: Describe how you will recruit your subjects? Attach a copy of any advertisement, flyer, letter, or statement that you will use for recruitment purposes.

Care providers (both professional and non-professional) whom have previously identified having interest in nighttime postural care training sessions at St. Catherine University or whom have considered NTPC as an intervention for their children/clients will be recruited for participation in the study. Care providers from two organizations (Gillette Children's Specialty Healthcare and LiveLife Therapy Solutions, Inc.) have already verbalized having interest in participation and will be invited to participate. Additionally, individual care providers (professional) from other organizations known to have interest in the NTPC intervention will also be invited.

A flyer will be sent via email to recruit participants for the study. This flyer will be/is attached to the application. Additionally the following script will be included in the body of the email.

"Hello (name), [As you know], I'm conducting a research study entitled "Nighttime postural care: Caregiver training and outcome measure feasibility" at St. Catherine University. I/We am/are trying to determine whether a training program I/we developed will be useful in preparing care providers (both non-professional and professional) to position and monitor children with cerebral palsy or movement limitations for sleep using sleep care positioning systems. I hope that you can participate by attending my/our sleep care positioning training session and completing a questionnaire rating the training. By participating in this research study you will attend a 4-8 hour training session and gain learning in a new sleep-based positioning intervention. You will also receive \$50/75 gift card and continuing education contact hours (if preferred by professional care providers). The gift card is being funded by St. Catherine University APDC grant # 00-1471-1.

"Also, if you are a professional care provider and know of any non-professional care providers (i.e. family member, care attendant, etc. of child with cerebral palsy whom might be a candidate for sleep-based positioning interventions) whom might be interested in participating in this study, please send their contact information (via encrypted email if verbal permission is given) to [name]"

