5. CONFIDENTIALITY OF DATA

a.	Will your	· data be anonyn	1ous?	
		Yes	X	No

(Anonymous data means that the researcher cannot identify subjects from their data, while confidential data means that the researcher can identify a subject's response, but promises not to do so publicly.)

b. How will you maintain anonymity/confidentiality of the information obtained from your subjects? Interview Example: I will assign pseudonyms to each interview participant. I will de-identify the data, and store the key separate from the recordings and transcripts. I will have the transcriptionist sign a confidentiality statement

Pseudonyms / code #s will be assigned to each participant. Data will be de-identified and a key that contains the name of the participant and their pseudonym/code along with any identifiable information / documents will be stored separately from the de-identified information / documents.

c. Data Storage: Where will the data be kept, and who will have access to it during that time? Examples: I will store audio files and electronic files on a password protected computer or cloud (indicate which; please avoid using flash drives as they are the one of the hardest 'tools' to protect and one of the easiest to exploit or lose, it is suggested to encrypt data on the cloud such as use a file password). I will store all paper files in a secure location (a locked filing cabinet) that is accessible only to myself and my advisor.

The pseudonym key and all paper files will be stored in a locked filing cabinet in the office of the primary investigator. Electronic files will be stored on the password protected computer of the primary investigator. Only the primary investigator will have key access to the paper files. Research assistants and co-investigators will have access to the files at the point of data collection and data analysis via primary investigator, then files will be returned by the primary investigator to the locked storage cabinet.

d. Data Destruction: How long will it be kept? What is the date when original data will be destroyed? (All studies must specify a date when original data that could be linked back to a subject's identity will be destroyed. Data that is stripped of all identifiers may be kept indefinitely). Example: I will destroy all records from the study within six months of the conclusion of the study but no later than June 2017.

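### Participants rate the PI's own training programme, and their own competence, on coded forms whose name key the PI also holds, so these self-ratings are at risk of courtesy bias.

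*Combined protocol and SAP*

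**What the plan says.** **What is rated.** In section 1d (Expectations of Participants), the post-training questionnaire has participants "rating their competence to implement aspects of the NTPC intervention and the quality and/or utility of the received training protocol". The post-simulation questionnaire asks for the same ratings again. Sub-question A of research question 1 (section 1c) is about perceived competence.

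**Whose programme.** The conflict-of-interest item in section 2 says that the programme was "developed through my dissertation work as well as in my role as master's project" advisor. The steps described there deal with the PI's outside consultancy, not with the PI evaluating a programme that the PI developed.

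**Who is invited, and how.** Section 3 starts from the two organisations: "A convenience sample of care providers from two different organizations have expressed" interest. It then adds "Other care providers known to the PI whom might be interested in this" study, with flyers in university health programmes as a fallback. The recruitment email in section 3a is in the PI's voice. It says that the study is to find out whether a "training program I/we developed will be useful in preparing care providers", and asks recipients to rate the training.

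**Who holds the data.** Section 5a says that the data are not anonymous. Section 5b says that the key and identifiable documents are kept apart from the de-identified ones. Section 5c says: "The pseudonym key and all paper files will be stored in a locked filing cabinet in the office of the primary investigator", and "Only the primary investigator will have key access to the paper files". Research assistants and co-investigators get the files through the PI for collection and analysis. Section 5e lists the PI, research assistants and student investigators as having the data.

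**How the ratings are analysed.** Section 1c (Data Analysis) names a paired t-test for within-group change in competence totals and sub-scores. It names no test for the quality ratings. The investigators code the open-ended comments.

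**The concern.** People asked to judge a programme by its developer, on forms that the developer can link to their names, may rate it more kindly than they otherwise would. The text describes no anonymous return, no collection by a third party and no other safeguard. Coding the forms gives little protection here, because the person holding the code is the person whose work is being rated.

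Baseline competence is rated before the programme has been seen, so any courtesy would enter mainly at the post ratings. It could then raise two results: the quality and utility ratings, and the pre-post change that the paired t-test examines. At stake is whether the programme is judged ready for the larger intervention study that this feasibility study is meant to inform. Participants with criticisms should be able to make them without the developer reading their named answers.

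**Working it through.** The plan gives no figure for this bias. It also gives no alpha, power, effect size or SD for its sample of 40, so there is no stated result to reproduce. The check has two parts.

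**1. Which results are exposed**

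| Source for question 1 | Where | Exposure to courtesy |
|---|---|---|
| Quality/utility ratings | 1d | Most direct: a judgement of the developer's product |
| Within-group change in self-rated competence | 1c, Data Analysis | Direct: no comparator inside the test |
| Self-rated competence compared between arms | Amendment form, items 1 and 2 | A lift shared by both arms cancels; a lift in one arm only does not |
| Quiz | Amendment form, item 1 | Less: a test of knowledge |
| Simulation scored by trained raters | 1c, Data Collection | Less: not self-report |

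The only between-group test that section 1c names compares professional with non-professional carers. Protection from the control arm therefore depends on the arms being compared, which the amendment intends but gives no test for.

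**2. What a lift would do to the t-tests (illustration only)**

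Assumptions, none of them from the documents: true effect zero, two-sided alpha 0.05, and a lift of d in units of the SD of change. The sample is either all 40 or one arm of 20 (equal allocation assumed).

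- Paired test: degrees of freedom n − 1, noncentrality d√n.
- Two-sample test with 20 per arm: degrees of freedom 38, noncentrality d√(20/2).
- Rejection probability: P(T > t_crit) + P(T < −t_crit), with T noncentral t.

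For d = 0.3 and n = 20, noncentrality is 0.3 × √20 = 1.342 and t_crit is 2.093 on 19 degrees of freedom. The rejection probability is 0.247.

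| Lift d | Paired, n = 20 | Paired, n = 40 | Two-sample, lift in trained arm only | Two-sample, lift equal in both arms |
|---|---|---|---|---|
| 0.1 | 0.071 | 0.095 | 0.061 | 0.05 |
| 0.2 | 0.136 | 0.235 | 0.095 | 0.05 |
| 0.3 | 0.247 | 0.457 | 0.152 | 0.05 |
| 0.5 | 0.565 | 0.869 | 0.338 | 0.05 |

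The paired test is the more vulnerable, and more so with a larger sample. These figures apply to competence scores only, since no test is planned for the quality ratings.

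**The case against.** Several stronger readings are tempting, and the documents do not support them.

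- *The raters are the PI's acquaintances.* Care providers known to the PI are one source. The two organisations come first, flyers are a fallback, and section 3a also seeks family carers through referral. The number who know the PI is not given. Acquaintance would strengthen courtesy, but the risk does not depend on it.
- *Only the PI keeps forms and key, and keeps them together.* Section 5b says that they are stored separately, and others get access for collection and analysis. What stands is that 5b and 5c pull in different directions, and that on either reading the PI has both.
- *The invitation asks for approval.* It does not. The email says that the investigators want to find out whether the programme is useful; the hope it expresses is that the recipient will take part.
- *Question 1 rests on these ratings.* It also draws on the quiz, the observed simulation and a randomised control group that is not told of the two-group design until after its post-questionnaire and demonstration. This limits the reach of the point. It does not remove it, because perceived competence in sub-question A is self-report by definition.
- *The ratings are inflated.* That is a risk, not an established fact. Courtesy depends on what raters believe about who reads their answers. The consent pages and questionnaires are not in the text reviewed, and the application says that confidentiality will be maintained.

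It can also be argued that the quality ratings have a comparator, because controls complete a post-questionnaire too. If the form is the same, that is partly true. But controls receive a handout of web links, so they would be rating a different product.

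**Conclusion.** The point holds as a risk to one strand of the evidence. Programme-quality ratings and within-group change in self-rated competence are collected under a code that the developer can open, and no safeguard is described. The quiz, the trained-rater observation and the between-arm comparison are less exposed.

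Neither the presence nor the size of a lift can be derived from the documents. On the assumptions above, a lift of 0.3 SD of change with no true effect makes the paired test significant in about 25% of studies at n = 20 and 46% at n = 40, against a nominal 5%. At 0.1 SD the figures are only 7% and 10%. The change is worth making because it is cheap and because modest lifts matter to an uncontrolled pre-post test. It does not call the whole feasibility conclusion into question.

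**What to change.** 1. Rewrite 5b and 5c so that they agree on where the key and the forms are kept and who can open each.
2. Have questionnaires returned under code number, online or in sealed envelopes, to one of the two planned research assistants. It should be one who did not train that participant, because the students from whom the assistants are drawn also help to finalise the programme and carry it out.
3. Have that assistant hold the name key apart from the forms until all data are entered. Give the PI coded data only.
4. Remove identifying details from open-ended comments before they are coded.
5. State in the consent script and on each questionnaire that the PI will not see any individual's identified answers.
6. Report the self-ratings alongside the between-arm quiz and simulation results.

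The cost is wording in 5b, 5c, the consent script and the questionnaire heads. Sample, sessions and instrument items do not change, and no staff are added. The downside is that the PI must resolve data queries through the assistant until entry is complete.

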5. CONFIDENTIALITY OF DATA

a.	Will your	· data be anonyn	1ous?	
		Yes	X	No

(Anonymous data means that the researcher cannot identify subjects from their data, while confidential data means that the researcher can identify a subject's response, but promises not to do so publicly.)

b. How will you maintain anonymity/confidentiality of the information obtained from your subjects? Interview Example: I will assign pseudonyms to each interview participant. I will de-identify the data, and store the key separate from the recordings and transcripts. I will have the transcriptionist sign a confidentiality statement

Pseudonyms / code #s will be assigned to each participant. Data will be de-identified and a key that contains the name of the participant and their pseudonym/code along with any identifiable information / documents will be stored separately from the de-identified information / documents.

c. Data Storage: Where will the data be kept, and who will have access to it during that time? Examples: I will store audio files and electronic files on a password protected computer or cloud (indicate which; please avoid using flash drives as they are the one of the hardest 'tools' to protect and one of the easiest to exploit or lose, it is suggested to encrypt data on the cloud such as use a file password). I will store all paper files in a secure location (a locked filing cabinet) that is accessible only to myself and my advisor.

The pseudonym key and all paper files will be stored in a locked filing cabinet in the office of the primary investigator. Electronic files will be stored on the password protected computer of the primary investigator. Only the primary investigator will have key access to the paper files. Research assistants and co-investigators will have access to the files at the point of data collection and data analysis via primary investigator, then files will be returned by the primary investigator to the locked storage cabinet.

d. Data Destruction: How long will it be kept? What is the date when original data will be destroyed? (All studies must specify a date when original data that could be linked back to a subject's identity will be destroyed. Data that is stripped of all identifiers may be kept indefinitely). Example: I will destroy all records from the study within six months of the conclusion of the study but no later than June 2017.

All records with identifiers will be destroyed one year after data collection and analysis is completed, by December 2019.

e. Availability of Data: Will data identifying subjects be made available to anyone other than you or your advisor? If yes, please explain who will receive the data, and justify the need. Example: The data will only be available to me and my advisor.

The data will only be available to the primary investigator, research assistants and MAOT student investigators.

f. Official Records: Will the data become a part of the medical or school record? If yes, explain.

NO

6. INFORMED CONSENT

a. How will you gain consent? State what you will say to the subjects to explain your research.

We will say the following to the potential participant: "You have expressed interest in participating in this research study. Before agreeing to participate we want to be sure you fully understand what you are being asked to do as a research participant. You have received the document entitled "ST CATHERINE UNIVERSITY Informed Consent for a Research Study". I will read the contents of the document aloud, then we'd like to hear your questions and/or concerns".

Then read document [ST CATHERINE UNIVERSITY Informed Consent for a Research Study].

"By signing this document you are officially agreeing to participate. Please do not sign until you feel you understand what to expect as a research participant and we've answered your questions and addressed your concerns. Also remember that at any time you can withdraw participation."

Gaining Assent from Children of Participants. Because participants are given the option of demonstrating the positioning of their child/client after the training/simulation, the assent of the child is needed. While the child/client is not the subject of the research, they still would need to agree to participate. Therefore, we will use the following script "We would like to see how your [name/title of care provider] positions you in this sleep system [show sleep system]. Please tell us if you are okay with [name of person] positioning you in the sleep system? Please answer yes if this is okay with you OR no if this is not okay with you. It is totally up to you". The script will be adjusted based on age level and ability to respond. For example if child is able to nod head yes or no, this might be used instead of a verbal response OR if able to use upper extremity to point to options yes / no, cards will be used for child to make selection. Additionally if child agrees and then during positioning shows facial expressions indicating discomfort or desire to end the activity, the positioning of child by caregiver will be stopped.

b. Consent Document: Attach the consent or assent form or text of oral statement. A template is available in Mentor IRB. Example: "See attached"

Consent document attached to the Mentor IRB application site.

c. Timing of Consent Process: Note: In studies with significant risk or volunteer burden, the IRB may require that subjects be given an interim period of 24 hours or more before agreeing to participate in a study

Once potential participants have expressed interest in participation, the consent form will be sent to them via email. At that time potential participants will be asked to review the document, consider any questions they may have and bring their questions with them to the session. The consent process will take place on the same day as the training session.

d. Assurance of Participant Understanding: How you will assess that the subject understands what they have been asked to do (Note: It is not sufficient to simply ask a yes/no question, such as "do you understand what you are being asked to do?")

We will ask potential participants to verbally communicate their understanding of the participant expectations, any concerns they have related to their ability to participate in any of the participant tasks and any concerns they have related to potential risks of participation.

We will use a modified list of questions from the UCSD Brief Assessment of Capacity to Consent (UBACC) during the consenting process.

Script: "We want to be sure we've been clear in explaining your role as a research participant. What is the purpose of the study that was just described to you? What makes you want to consider participating in this study? If you participate in this study, what are some of the things you will be asked to do? Do you have to be in this study if you do not want to participate? Please describe some of the risks or discomforts that people may experience if they participate in the study? Do you feel you may be unable to complete the activities or be at risk of injury? Is it possible that this study will not have any benefit to you? Please describe some of the benefits of this study? Who will pay for medical care if you are injured as a direct result of participating in this study?"

If the responses to the above questions show the potential participant is unclear about their role in the research study, we will provide clarifying information and repeat the questions after the clarifying information has been provided.

- 7. CITI TRAINING Work with your faculty advisor or contact [contact] if you have any questions about whether you should complete additional training modules within CITI. You can also reference the HSR Mandatory Education Policy: https://www.stkate.edu/pdfs/irb-human-subject-research-education.pdf
 - a. Select all the CITI training courses/modules you completed:

REQUIRED COURSE:
Human Subject Research Training Course – only one course is required
Human Subject Research - Social & Behavioral Research Investigators
Human Subject Research - Education Action Research Program
X Human Subject Research - Biomedical Research Investigators
OPTIONAL MODULES:
Financial Conflict of Interest Course (suggested if you answered YES to Section 2 part g)
Avoiding Group Harms - U.S. Research Perspectives (suggested if you checked any special populations in Section 2 part e)
International Research (suggested for PIs doing research outside of the US that is NOT federally funded)
International Studies (suggested for PIs doing research outside of the US that IS federally funded)
Cultural Competence in Research (suggested when conducting research across cultures, i.e. with a population that is culturally different from one's own)
Internet Based Research (suggested for PIs using internet resources during their research (outside of recruitment) – Skype, survey tools, internet activity monitoring, etc)
Other (prisoners, pregnant women, children):

